Dermatology Life Quality Index (DLQI)

The DLQI is calculated by summing the score of each question resulting in a maximum of 30 and a minimum of 0. The higher the score, the more quality of life is impaired. If one question is unanswered, this is allocated a score of 0 for the purpose of summing to the DLQI score. If two or more questions are unanswered, the questionnaire is not scored.

Each question is answered on a Likert scale: Very much=scored 3, A lot=scored 2, A little= scored 1, Not at all= scored 0, Not relevant=scored 0, Question Not Answered=0. Question 7 is asked in two parts. The first part asks if the skin disease has ‘prevented you from working or studying’. If skin disease has prevented working or studying, then Question 7 is scored 3. If working or studying are not relevant, the response is Not relevant and scored 0. If the answer is No, then Question 7 is scored based on the second part of the question as to ‘How much has your skin been a problem at work or studying’: ‘A lot’(scored 2), ‘A little’ (scored 1) or ‘Not at all’ (scored 0).

Treatment-Emergent Adverse Event (TEAE)

TEAEs are defined as AEs with an onset date on or after the date of first administration of study drug and before the date of last administration of study drug + 30 days.

Treatment-Emergent Laboratory Abnormalities

A treatment-emergent laboratory abnormality is defined as a result in which the baseline value is within normal laboratory limits and the post-baseline value is outside normal laboratory limits. If the relevant baseline assessment is missing, then any post-baseline value outside normal laboratory limits will be considered a treatment-emergent value.

Treatment-emergent Laboratory Toxicity

A treatment-emergent laboratory toxicity is defined as an increase of at least one toxicity grade from the baseline assessment at any post baseline visit. If the relevant baseline assessment is missing, then any graded abnormality (i.e., at least Grade 1) is considered to be treatment-emergent.

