### **5.5.2. Clinical Laboratory Assessments and Vital Signs**

Laboratory data (hematology, serum chemistry, coagulation, FSH and urinalysis) will be converted to Système International (SI) units for reporting and processing purposes.

Descriptive summaries of absolute values of quantitative clinical laboratory results and their change from baseline values will be presented by analysis visit and treatment group. Observed values of categorical urinalysis data will be displayed with frequencies and percentages. All laboratory data will be listed for individual patients.

Treatment-emergent abnormal laboratory assessments will be based on the lab provided normal ranges. If the baseline laboratory assessment is normal and shifts to Low or High post-baseline, then the laboratory value is considered a TE abnormal laboratory value. If the baseline laboratory assessment is Low and shifts to High post-baseline or the baseline laboratory assessment is High and shifts to Low post-baseline, then the laboratory value is considered a TE abnormal laboratory

value. For each protocol specified lab test, the number and percent of patients reporting a TE abnormal lab will be reported.

For CK, Absolute Neutrophils, ALT, AST, and Bilirubin, laboratory abnormalities will be graded via the Common Terminology Criteria for Adverse Event (CTCAE) version 5.0. A summary of treatment-emergent laboratory toxicities for the indicated laboratory results by maximum CTCAE toxicity grades will be reported.

All laboratory summaries will be limited to the tests specified in the protocol.

Descriptive summaries of vital signs, weight, and BMI and their change from baseline will be presented by study visit and treatment group and all vital signs will be listed.

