## **Section 14.3 Safety**

Table 14.3.1.1 Overall Summary of Adverse Events, Safety Population

Table 14.3.1.2 Treatment-Emergent Adverse Events by System Organ Classification, Preferred Term and Greatest Severity, Safety Population

Table 14.3.1.3 Treatment-Emergent Adverse Events by System Organ Classification and Preferred Term, Safety Population

Table 14.3.1.4 Treatment-Emergent Serious Adverse Events by SOC and PT, Safety Population

Table 14.3.1.5 Treatment-Emergent Adverse Events Related to Study Drug by SOC and PT, Safety Population

Table 14.3.1.6 Treatment-Emergent Adverse Events Leading to Discontinuation of Study Drug by SOC and PT, Safety Population

Table 14.3.1.7 Study Drug Related Treatment-Emergent Adverse Events Leading to Discontinuation of Study Drug by SOC and PT, Safety Population

Table 14.3.1.8 Adverse Events of Special Interest (AESI) by SOC and PT, Safety Population

Table 14.3.1.9 Summary of Most Frequent Treatment Emergent Adverse Events by Preferred Term, Safety Population

Table 14.3.4.1.1 Summary of Hematology and Coagulation Results and Change from Baseline by Analysis Visit, Safety Population

Table 14.3.4.1.2 Summary of Serum Chemistry Results and Change from Baseline by Analysis Visit, Safety Population

Table 14.3.4.1.3 Summary of Urinalysis Results and Change from Baseline by Analysis Visit, Safety Population

Table 14.3.4.2.1 Summary of Treatment-Emergent Abnormal Hematology and Coagulation by Analysis Visit Safety Population

Table 14.3.4.2.2 Summary of Treatment-Emergent Abnormal Serum Chemistry by Analysis Visit, Safety Population

Table 14.3.4.2.3 Summary of Treatment-Emergent Abnormal Urinalysis by Analysis Visit, Safety Population

Table 14.3.4.4 Summary of Laboratory Results by CTCAE Toxicity Grades for CK, Absolute Neutrophils, ALT, AST, and Bilirubin, Safety Population

---

Table 14.3.5.1 Summary of Vital Signs and Change from Baseline by Analysis Visit, Safety Population

Table 14.3.5.2.1 Summary of ECG Results and Change from Baseline by Analysis Visit, Safety Population

Table 14.3.5.2.2.1 Proportion of Patients with Abnormal Investigator ECG Interpretations by Analysis Visit, Safety Population

Table 14.3.5.2.2.2 Proportion of Patients with Abnormal Central ECG Interpretations by Analysis Visit, Safety Population

Table 14.3.5.2.3 Proportion of Patients with Noteworthy QT Changes by Analysis Visit, Safety Population

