#### **Listings**

Listing 16.2.1 Subject Disposition and Reasons for Early Termination FAS Population

Listing 16.2.2 Protocol Violations FAS Population

Listing 16.2.3 Study Populations FAS Population

Listing 16.2.4.1 Demographics FAS Population

Listing 16.2.4.2 Medical History FAS Population

Listing 16.2.5.1.1 Dosing Diary Safety Population

Listing 16.2.5.1.2 Study Drug Accountability Safety Population

Listing 16.2.5.2 Prior and Concomitant Medications FAS Population

Listing 16.2.5.3 Pharmacokinetics at Scheduled Collection Times, PK Population

Listing 16.2.6.1 Lesion Count, Hurley Stage, HiSCR Responder, and HIS-4 Score, FAS Population

Listing 16.2.6.2 Patient's Global Assessment of Skin Pain (PGA-SP), FAS Population

Listing 16.2.6.3 Hidradenitis Suppurativa-Physician's Global Assessment (HS-PGA), FAS Population

---

- Listing 16.2.6.4 Dermatology Life Quality Index (DLQI), FAS Population
- Listing 16.2.7.1 Adverse Events Safety Population
- Listing 16.2.7.2 Related Adverse Events, Safety Population
- Listing 16.2.7.3 Serious Adverse Events, Safety Population
- Listing 16.2.7.4 Adverse Events Leading to Discontinuation, Safety Population
- Listing 16.2.7.5 Adverse Events of Special Interest, Safety Population
- Listing 16.2.8.1.1 Laboratory Tests – Serum Chemistry FAS Population
- Listing 16.2.8.1.2 Laboratory Tests – Hematology and Coagulation, Safety Population
- Listing 16.2.8.1.3 Laboratory Tests – Urinalysis, Safety Population
- Listing 16.2.8.1.4 Laboratory Abnormalities, Safety Population
- Listing 16.2.8.1.5 Laboratory Tests – Serum and Urine Pregnancy Test Results, Safety Population
- Listing 16.2.8.1.6 Laboratory Tests – Other Tests, Safety Population
- Listing 16.2.8.2 Vital Signs, Safety Population
- Listing 16.2.8.3 Physical Examination, Population
- Listing 16.2.8.4 Electrocardiogram, Safety Population

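### A laboratory value already out of range at Baseline that worsens in the same direction is never treatment-emergent under the SAP, and outside five CTCAE-graded tests no rule-based incidence by arm captures it

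*SAP*

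**What the plan says.** The SAP has two rules for laboratory values that become abnormal on treatment.

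The first covers all tests. SAP 3.3.8 says: "A treatment-emergent laboratory abnormality is defined as a result in which the baseline value is within normal laboratory limits", and requires the post-baseline value to be outside those limits. If Baseline is missing, any out-of-range post-baseline value counts. SAP 5.5.2 restates the rule and adds shifts across the range: "If the baseline laboratory assessment is Low and shifts to High post-baseline", and the reverse. Its scope is broad: "For each protocol specified lab test, the number and percent of patients reporting a TE abnormal lab will be reported". The results go into Tables 14.3.4.2.1 to 14.3.4.2.3. The first of these is titled "Summary of Treatment-Emergent Abnormal Hematology and Coagulation by Analysis Visit", and the other two do the same for chemistry and urinalysis.

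The second rule concerns toxicity grades. SAP 3.3.8 defines a treatment-emergent toxicity as "an increase of at least one toxicity grade from the baseline assessment at any post baseline visit". SAP 5.5.2 limits grading to five tests: "For CK, Absolute Neutrophils, ALT, AST, and Bilirubin, laboratory abnormalities will be graded via the Common Terminology Criteria". The matching output is Table 14.3.4.4, "Summary of Laboratory Results by CTCAE Toxicity Grades for CK, Absolute Neutrophils, ALT, AST, and Bilirubin, Safety Population".

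The remaining laboratory output is descriptive statistics for values and changes, frequencies for categorical urinalysis results, plots for the five graded tests, and listings, among them Listing 16.2.8.1.4, "Laboratory Abnormalities, Safety Population". Protocol Table 2 makes the incidence of laboratory abnormalities a secondary endpoint.

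**The concern.** A rule that depends on Baseline being normal cannot register a patient who enters slightly out of range and then gets clearly worse. The sponsor anticipated this for five tests, where the grade rule looks at the size of the move and not at whether Baseline was normal. The other tests have no such second rule.

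The situation can arise in this trial. Inclusion criterion 9 admits out-of-range Screening results that the investigator considers not clinically significant. Exclusion criterion 8 removes only values beyond fixed limits, for example haemoglobin below 10 g/dL. What is at stake is the completeness of a declared secondary safety endpoint for patients who start out of range. Efficacy is not involved.

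**Working it through.** The documents state no figure on this point, so there is none to reproduce. The check is an enumeration of the rule, followed by a search of the planned outputs.

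**Step 1: which pairs count.** The inputs are the definition in SAP 3.3.8 and the shifts in SAP 5.5.2. Four Baseline states by three post-baseline states give 4 × 3 = 12 pairs.

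| Baseline | Later Low | Later Normal | Later High |
|---|---|---|---|
| Low | not counted | not counted | counted (5.5.2 only) |
| Normal | counted (both) | not counted | counted (both) |
| High | counted (5.5.2 only) | not counted | not counted |
| Missing | counted (3.3.8 only) | not counted | counted (3.3.8 only) |

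Six pairs count under at least one text, which leaves 12 − 6 = 6 that do not. Four of these six end in the normal range and rightly do not count. The other two, Low to Low and High to High, end out of range and are uncounted under both texts, however large the worsening.

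**Step 2: does another planned rule catch those two pairs?**
- Table 14.3.4.4 does when a grade boundary is crossed, but only for CK, neutrophils, ALT, AST and bilirubin.
- The laboratory-based events of special interest in SAP 5.5.1 concern CK and neutrophils, which are already among the five.
- The table list in SAP section 9 contains no shift table and no further grade table.

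For every other test, the number of rule-based tables by arm that can count same-direction worsening is zero.

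**Step 3: what still shows it.**
- Change from Baseline by visit and arm includes the minimum and maximum (SAP section 5). An extreme individual change is visible, but not how many patients worsened. Under SAP 3.3.9 these summaries use the result nearest the target day, so a worse unscheduled value further from that day appears only in the listings.
- Listings show each patient's results but give no incidence.
- Protocol 8.2.4 sends clinically relevant laboratory changes to the adverse event pages. If treatment-emergent, they then enter tables by arm by system organ class and preferred term. Entry depends on investigator judgement.

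**Step 4: an example.** Take a patient who enters with haemoglobin at or just above 10 g/dL, assuming the laboratory's lower normal limit is higher (the reference ranges are not in the documents). The patient is eligible if the result is judged not clinically significant. If haemoglobin then falls well below 10 g/dL, the pair is Low to Low. It adds nothing to Table 14.3.4.2.1, and Table 14.3.4.4 does not include haemoglobin.

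**The case against.** The strongest reply is that the five graded tests are a deliberate choice. They cover the protocol's laboratory stopping areas (liver function, neutrophils and CK, in Protocol 7.1.1 to 7.1.3). Two of them define events of special interest, and all five are plotted in SAP 5.5.4. The SAP thus grades where the protocol locates the risk and reports new abnormalities elsewhere. Protocol 9.4.2 promises only descriptive summaries and listings for laboratory data, so no commitment is broken. Exclusion criterion 9 also removes clinically significant abnormalities that would affect safety or interpretation, so those who enter out of range should mostly be minor cases.

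Much of this stands. It explains the choice of five tests and shrinks the pool. It does not make the treatment-emergent table count worsening in the other tests.

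A reader might infer more than the documents support, in three ways.
- That such worsening would go unseen. It would not: the outputs in step 3 remain, and an independent DSMB reviews unblinded safety data (Protocol 9.6).
- That the reported incidences are too low by some calculable amount. The documents give neither the share of patients out of range at Baseline nor any rate of worsening.
- That the percentages are diluted because patients already abnormal stay in the denominator. SAP 5.5.2 does not say that Low and High get separate rows, and without them a patient Low at Baseline can still count by moving to High. The default denominator is also the number with a value at the visit, not a fixed arm size.

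**Conclusion.** The gap is real and small. Same-direction worsening from an abnormal Baseline is never a treatment-emergent abnormality for any test, and outside the five graded tests no rule-based incidence by arm captures it. For a given test, the number of patients missed lies between zero and the number who start out of range in that direction; neither the latter nor the share who worsen can be derived from the documents. The primary conclusion is unaffected, and clinically relevant cases can still reach the adverse event tables by arm. This is an inexpensive improvement to a secondary safety endpoint, not a defect in patient protection.

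The conclusion rests on the visible definitions and the visible list of outputs. SAP 3.3.7 and part of SAP section 6 are redacted, the content of Listing 16.2.8.1.4 is not described, and the protocol appendices with the test list and the adverse event definitions are not among the documents.

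**What to change.** In SAP 5.5.2, apply the grade-increase rule already in SAP 3.3.8 to haemoglobin, platelets, WBC and lymphocytes, where CTCAE v5.0 grades them, and add these tests to Table 14.3.4.4. State that the worst post-baseline value is used, including unscheduled results.

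If further CTCAE grading is not wanted, report by arm the number of patients whose worst post-baseline value crosses the limits in exclusion criterion 8: haemoglobin <10 g/dL, platelets <100 × 10³, WBC <3.0 × 10³ and lymphocytes <0.5 × 10³ cells/mm³. Because those limits apply at Screening, show Baseline status beside the count, so that a patient already beyond a limit on Day 1 is recognisable.

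Neither option is complete. Worsening within a grade, or short of a limit, remains visible only in the Step 3 outputs, and the second option looks only at low values. The same edit could align SAP 3.3.8 with 5.5.2, since shifts across the range appear only in 5.5.2 and the missing-Baseline rule only in 3.3.8.

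The cost is SAP wording and one longer or additional safety table from data already collected.

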### **3.3.9. Presentations by Study Visit**

Scheduled and unscheduled assessments collected from Visit 1 through Visit 8 for all efficacy assessments and safety assessments (labs, vital signs, and ECG) will be assigned to an analysis visit window using the study day ranges described in [Table 1](#) and [Table 2](#). All study days up to and

---

including Day 1 are in the baseline-eligible analysis visit window. The last non-missing assessment in the baseline-eligible analysis visit window will be used in any summaries that present the baseline results with the exception of ECG interpretation where the best result from the triplicate values will be chosen. Day 1 post-dose ECG, PK and vital signs assessments will be analyzed as collected. Day 8 ECG assessments, Day 8 and 85 PK assessments, and Day 8, 15, 29, 43, 57 and 85 vital sign assessments will be windowed per Table 2, then each time point will be analyzed as collected. For all other assessments, for post-baseline analysis windows, if multiple assessments occur within a given analysis visit window, the result closest to the target study day, regardless of whether scheduled or unscheduled, will be used for summary presentations. If two measurements have the same distance to the target study day, the first assessment will be used in the summary presentations with the exception of ECG interpretation where the worst result from the triplicate values for the given visit and timepoint will be used. All assessments will be presented in the listings. In addition to the analysis visits indicated in Table 1 and Table 2, for patients who prematurely discontinue the study, data collected during the withdrawal visit will be used as an EOS assessment for these patients. The EOS assessment will be included in safety analyses.

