#### **5.5.3. Other Safety Analyses**

ECG measurements will include heart rate, QT interval, Fredericia-corrected QT interval (QTcF), PR interval, and QRS interval. Triplicate ECG values will be obtained at each time point. Summary tables will present the average of the triplicate ECG results. ECG results and their change from baseline values will be summarized descriptively by treatment group at each scheduled evaluation and all ECG data will be listed. Proportion of patients with abnormal ECG interpretations will be summarized at each study visit and by treatment group for both investigator and central interpretation. Proportion of patients who meet each of the following criteria based on triplicate averages from International Conference on Harmonization Guideline E14 “Clinical Evaluation of QT/QTc Interval Prolongation and Proarrhythmic Potential for Non-Antiarrhythmic Drugs” (October 2005) for QT and corrected QT intervals will be summarized across treatment groups:

- QTcF >450 msec
- QTcF >480 msec
- QTcF >500 msec
- QTcF increases from baseline by >30 msec
- QTcF increases from baseline by >60 msec

The above summaries will be repeated for QT.

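### ECG interpretation uses the best of three tracings at baseline and the worst of three afterwards, so the two abnormal-ECG tables will show an artificial rise from baseline in both arms

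*SAP*

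**What the plan says.** SAP 5.5.3 states that "Triplicate ECG values will be obtained at each time point". SAP 3.3.9 then chooses which of the three readings stands for the patient.

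- **Baseline.** The last non-missing assessment in the baseline window is "used in any summaries that present the baseline results", except for "ECG interpretation where the best result from the triplicate values will be chosen".
- **After baseline.** When two measurements are equally far from the target day the first is used, except for "ECG interpretation where the worst result from the triplicate values for the given visit and timepoint will be used".

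The worst-of-three clause sits in a tie-break sentence. The three tracings of a set share one visit and time point, so they always tie and the clause applies to every triplicate that the sentence covers. Days 15 to 85 are plainly covered. For Day 1 post-dose and Day 8, the same section says that ECGs are analysed as collected, which leaves the selection rule unclear.

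The selected reading feeds one summary in SAP 5.5.3: "Proportion of patients with abnormal ECG interpretations will be summarized at each study visit and by treatment group for both investigator and central interpretation". The outputs listed in SAP section 9 are Table 14.3.5.2.2.1, "Proportion of Patients with Abnormal Investigator ECG Interpretations by Analysis Visit, Safety Population", and Table 14.3.5.2.2.2, "Proportion of Patients with Abnormal Central ECG Interpretations by Analysis Visit, Safety Population". Baseline is one of the analysis visits in SAP Table 2.

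Numeric ECG results are handled differently: "Summary tables will present the average of the triplicate ECG results". The SAP revision history records that the selection rule was added. The visible text gives no reason for using opposite rules.

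**The concern.** A by-visit table invites the reader to compare each visit with baseline. Here the definition of abnormal changes between the two, from all three tracings to any one of three. A patient whose ECG never changes, but whose tracings are sometimes read differently from one another, can be normal at baseline and abnormal at every later visit through the rule alone.

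The incidence of ECG abnormalities is a secondary endpoint (Protocol section 3.0, Table 2), and these are the two planned tables that report abnormal ECG readings. If the rise in each arm is partly or wholly produced by the rule, the change from baseline in those tables cannot be taken at face value.

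**Working it through.** **Inputs.** There are three tracings per time point (SAP 5.5.3), opposite selection rules (SAP 3.3.9) and about 45 patients per arm (SAP 1.1). The plan states no figure on this point, so there is none to reproduce. Two quantities are missing from the documents and are assumed over a range:

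- q, the probability that a single tracing is read as abnormal;
- ρ, the correlation between readings within a triplicate.

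Both are held equal at baseline and afterwards, meaning no drug effect and no time effect.

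**Independent reads (ρ = 0).**

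- Best of three is abnormal with probability q³. At q = 0.10 this is 0.001, or 0.1%.
- Worst of three is abnormal with probability 1 − (1 − q)³. At q = 0.10 this is 1 − 0.729 = 0.271, or 27.1%.
- The rise is 27.0 points, about 12 of 45 patients.

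**Correlated reads (beta-binomial).** Put s = (1 − ρ)/ρ, a = qs and c = (1 − q)s. Then

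- P(all three abnormal) = a(a+1)(a+2) / [s(s+1)(s+2)]
- P(none abnormal) = c(c+1)(c+2) / [s(s+1)(s+2)]

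At q = 0.10 and ρ = 0.5, s = 1, a = 0.1 and c = 0.9:

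- best of three: 0.1 × 1.1 × 2.1 / 6 = 0.0385
- worst of three: 1 − 0.9 × 1.9 × 2.9 / 6 = 1 − 0.8265 = 0.1735
- rise: 13.5 points, about 6 of 45 patients

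At ρ = 0.8 the same formulas give 7.4% and 12.8%, a rise of 5.4 points, about 2 of 45 patients.

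**A shortcut that shows what drives the size.** Worst minus best is the probability that the three readings are not all alike. A triplicate in disagreement always contains exactly two discordant pairs out of three, and each pair is discordant with probability 2q(1 − q)(1 − ρ). The rise is therefore 3 × 2q(1 − q)(1 − ρ) / 2 = 3q(1 − q)(1 − ρ). Check: 3 × 0.1 × 0.9 × 0.5 = 0.135.

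Artificial rise, in percentage points:

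| q | ρ = 0 | ρ = 0.5 | ρ = 0.8 | ρ = 0.9 | ρ = 1 |
|---|---|---|---|---|---|
| 5% | 14.3 | 7.1 | 2.9 | 1.4 | 0 |
| 10% | 27.0 | 13.5 | 5.4 | 2.7 | 0 |
| 20% | 48.0 | 24.0 | 9.6 | 4.8 | 0 |

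**Under a single rule.** The expected rise with no true change is 0 for every q and ρ. At q = 10% with independent reads, worst of three gives 27.1% at both times, a two-of-three majority gives 2.8% at both, and best of three gives 0.1% at both.

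**Between arms at a visit.** Both arms use worst of three after baseline, so equal q gives equal expected proportions. If single-read rates were 20% and 10%, a gap of 10 points, worst of three would give:

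- ρ = 0: 48.8% against 27.1%, a gap of 21.7 points
- ρ = 0.5: 32.8% against 17.4%, a gap of 15.5 points before rounding
- ρ = 0.8: 24.9% against 12.8%, a gap of 12.1 points

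**The case against.** The case for leaving the rule alone has real substance.

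- **The trial has a concurrent placebo arm.** The natural safety comparison is arm against arm at a visit, and with no drug effect the rule does not bias it. No shift table or treatment-emergent count of ECG interpretations is listed. This stands, and it confines the harm to change from baseline within an arm.
- **The size may be small.** Protocol 8.2.3 has the three tracings taken in close succession from a resting patient, in less than 4 minutes. High agreement is plausible, and the right-hand columns of the table may be nearer the truth than the left. This also stands, but the rise disappears only if tracings are never read differently.
- **Worst of three is a cautious safety screen, and all tracings remain in the listings.** That supports worst of three after baseline. It does not support pairing it with best of three at baseline, because worst of three throughout is equally cautious after baseline.

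Two stronger readings are tempting, and the documents support neither.

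- **That the QTcF safety read-outs are distorted.** The rule covers ECG interpretation only. Mean ECG values and the QT/QTcF threshold counts use triplicate averages (SAP 5.5.3), as do the interruption criteria in Protocol 7.2.2. The QTcF event of special interest in SAP 5.5.1 uses the same two thresholds, and nothing ties it to the best or worst reading.
- **That the rule hides a drug effect by weakening the contrast between arms.** In the worked example the gap widens at each correlation. With independent reads the slope of 1 − (1 − q)³ is 3(1 − q)², which exceeds 1 while q is below 1 − 1/√3, about 0.42. Only at higher abnormal rates would the contrast shrink.

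**Conclusion.** The concern holds in a limited form, and its severity is minor. As written, the SAP will produce an artificial rise from baseline in the proportion with an abnormal ECG interpretation, in both arms and in both tables, whenever tracings within a triplicate are read differently. The direction is certain; the size is not. At an assumed 10% single-tracing rate it runs from 27 points (independent reads) through 13.5, 5.4 and 2.7 points (correlation 0.5, 0.8 and 0.9) to 0 at perfect agreement.

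This rests on three assumptions: interpretations are recorded per tracing, as the SAP rule presupposes; the tables show a baseline row, as the analysis visits suggest (no table shells are available); and single-tracing rates are the same at both times.

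Two points could change what is seen. If best is taken over every triplicate in the baseline window, and not only the last pre-dose set, the gap widens. Separately, exclusion criterion 22 removes some patients with abnormal baseline ECGs, so baseline may look cleaner for a reason unrelated to this rule.

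**What to change.** Replace the two exceptions in SAP 3.3.9 with one sentence: for ECG interpretation, the worst reading of the triplicate is used at baseline (stating which pre-dose triplicate is meant) and at every post-baseline visit and time point, including Day 1 post-dose and Day 8, for both the investigator and the central tables.

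This leaves the post-baseline proportions at Days 15 to 85 as they are now, keeps the safety sensitivity and brings the expected artefact to zero. A two-of-three majority at every time point would also remove it, but would flag fewer patients. If the opposite rules are kept, give the reason and footnote both tables to say that the baseline and post-baseline proportions are defined differently and should not be subtracted.

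The cost is one sentence and a small programming change, with no new data and no effect on the primary analysis. The downside is that the baseline abnormal proportion will look higher: at a 10% rate and correlation 0.5, it would be 17.4% in place of 3.9%.
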